3.9 DATA AND SAFETY MONITORING

This trial will be monitored in accordance with the sponsor's Pharmacovigilance Committee procedures. Adverse events and SAEs will be reviewed internally on an ongoing basis to identify safety concerns. Quarterly conference calls with the investigators will be conducted to discuss study progress, obtain investigator feedback and exchange, and discuss "significant safety events" (ie, AEs leading to dose reductions, related SAEs, and deaths).

4.0 STUDY ACTIVITIES AND ASSESSMENTS

The schedule of events is provided in [Appendix 4](#). Descriptions of the scheduled evaluations are outlined below and complete information on study drug and dosing is provided in [Section 3.5](#).

Before study entry, throughout the study, and at the follow-up evaluation, various clinical and diagnostic laboratory evaluations are required. The purpose of obtaining these detailed measurements is to ensure adequate safety and tolerability assessments. Clinical evaluations and laboratory studies may be repeated more frequently if clinically indicated. Such unscheduled assessments will be captured in the protocol-specific database as appropriate.

4.1 DESCRIPTION OF PROCEDURES

4.1.1 Informed Consent

The subject must read, understand and sign the IRB/IEC approved ICF confirming his or her willingness to participate in this study before initiating any screening activity that is not standard of care. Subjects must also grant permission to use protected health information.

4.1.2 Medical History

Collect and record the subject's complete history through review of medical records and by interview. Concurrent medical signs and symptoms must be documented to establish baseline severities. A disease history, including the date of initial diagnosis and list of all prior anticancer treatments, and responses to these treatments, also will be recorded.

4.1.3 Adverse Events

The accepted regulatory definition for an AE is provided in [Section 6.1](#). All medical occurrences from the time of first dose that meet this definition must be recorded. Important additional requirements for reporting SAEs are explained in [Section 6.2](#).

4.1.4 Concomitant Medications and Therapy

Document all concomitant medications and procedures from within 21 days before the start of study drug administration through 30 days after the last dose of study drug.

4.1.5 Confirmation of Eligibility

Subject eligibility for enrollment will be assessed per [Section 3.4](#). All screening procedures, unless otherwise indicated, should be completed within 21 days of the first dose of study drug. De-identified copies of all screening radiology results, site pathology report for confirming diagnosis of ABC DLBCL, and a list of prior anticancer therapy and best responses need to be submitted to the sponsor as part of the enrollment process.

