| Pharmacokinetic Parameters: | 
The plasma PK of acalabrutinib will be characterized using noncompartmental analysis. The following PK parameters will be calculated, whenever possible, from plasma concentrations of acalabrutinib:
 
 • AUC_{0-t}: Area under the plasma concentration-time curve calculated using linear trapezoidal summation from time 0 to time t, where t is the time of the last measurable concentration (C_t). • AUC_{0-12}: Area under the plasma concentration-time curve from 0 to 12 hours, calculated using linear trapezoidal summation. • $AUC_{0-\infty}$: Area under the plasma concentration-time curve from 0 to infinity, calculated using the formula: $AUC_{0-\infty} = AUC_{0-t} + C_t / \lambda_z$, where λ_z is the apparent terminal elimination rate constant. • $AUC_{0-24calc}$: Area under the plasma concentration-time curve from 0 to 24 hours, calculated by doubling the value for AUC_{0-12}. • C_{max}: Maximum observed plasma concentration • T_{max}: Time of the maximum plasma concentration (obtained without interpolation) • $t_{1/2}$: Terminal elimination half-life (whenever possible) • λ_z: Terminal elimination rate constant (whenever possible) • CL/F: Oral clearance |
| Pharmacodynamic Parameters: | 
The occupancy of Btk by acalabrutinib will be measured in peripheral blood mononuclear cells (PBMCs) with the aid of a biotin-tagged acalabrutinib analogue probe. The effect of acalabrutinib on biologic markers of B-cell function will also be evaluated.
 |
| Sample Size: | 
Twenty subjects that consist of 10 subjects who are refractory to and 10 subjects who have relapsed from the previous anticancer therapy.
 |
| Inclusion Criteria: | 
 • Men and women ≥ 18 years of age. • Eastern Cooperative Oncology Group (ECOG) performance status of ≤ 2. • Pathologically confirmed de novo ABC DLBCL, and subjects must have available archival tissue for central pathology review to be eligible. • Relapsed or refractory disease, defined as either: 1) recurrence of disease after a CR, |

| | |
|--|--|

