1.2 ROLE OF BTK IN LYMPHOID CANCERS

Bruton tyrosine kinase (Btk) is a non-receptor enzyme of the Tec kinase family that is expressed among cells of hematopoietic origin, including B cells, myeloid cells, mast cells and platelets, where it regulates multiple cellular processes including proliferation, differentiation, apoptosis, and cell migration (Mohamed 2009, Bradshaw 2010). Functional null mutations of Btk in humans cause the inherited disease, X-linked agammaglobulinemia, which is characterized by a lack of mature peripheral B cells (Vihinen 2000). Conversely, Btk activation is implicated in the pathogenesis of several B-cell malignancies (Buggy 2012). Taken together, these findings have suggested that inhibition of Btk may offer an attractive strategy for treating B-cell neoplasms.

Ibrutinib (IMBRUVICA™), a first generation oral, small-molecule Btk inhibitor has been approved for the treatment for CLL and MCL. Interim results from a Phase 2 study of ibrutinib 560 mg QD in subjects with relapsed/refractory GCB and ABC DLBCL reported an objective tumor response rate of 41% (CR 17% and PR 24%) for subjects with ABC DLBCL (N=29) versus 5% (no CRs) in subjects with GCB DLBCL (N=20) (de Vos 2013). In a Phase 1 dose-escalation study (160 to 480 mg QD) of ONO-4059, a second generation Btk inhibitor, in subjects with ABC DLBCL an ORR of 47% (7/15) was observed (Dyer 2014). Also subjects who were refractory to the prior anticancer therapy had an ORR of 33% (3/9) compared with an ORR of 67% (4/6) for subjects who had relapsed after the prior therapy. In both studies, the Btk inhibitors were well tolerated.

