3.4.4 Enrollment Procedures

Enrollment of a subject into the study will be performed according to the following procedure:

- The study center will notify the sponsor when a clinically eligible subject is identified and is ready to screen, to ensure enrollment availability on the study.
- After the subject has signed and dated the Informed Consent Form (ICF), all screening procedures have been completed, and eligibility has been confirmed, the subject can be officially enrolled in the study.
- To enroll a subject, the study center will fax/email a completed Enrollment Confirmation Form to the sponsor. The enrollment date will be the date that the form is faxed/emailed to the sponsor.
- An Enrollment Confirmation Form will be completed and faxed/emailed to the study center by the sponsor within 24 hours.

Treatment must begin within the screening window ([Section 4.1](#)) and after the site has received notification from the sponsor. Study treatment is not blinded on this study.

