4.1.6 Archival Tumor Sample

All subjects must have available archival tissue for central pathology review. Either unstained slides (minimum of 10 slides) or a paraffin block will be acceptable for central pathology review. Please refer the study manual for a more detailed description of the procedures and for information on where to send the archival tissue samples.

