5.2 DEFINITION OF ANALYSIS SETS

The following definitions will be used for the efficacy and safety analysis sets.

Safety analysis set: All enrolled subjects who receive ≥ 1 dose of study drug.

Per-protocol (PP) analysis set: All enrolled subjects who receive ≥ 1 dose of study drug, have sufficient baseline measurements, and undergo ≥ 1 assessment for the endpoint of interest (eg, response and PK/PD parameters) after treatment.

Intent-to-treat (ITT) population: All subjects who have enrolled in the protocol.

The safety analysis set will be used for evaluating the safety and efficacy, except duration of response, parameters in this study. The PP and ITT analysis sets will be analyzed for efficacy and PK/PD parameters in this study.

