5.4 DETERMINATION OF SAMPLE SIZE

No formal statistical tests of hypotheses will be performed. Descriptive statistics (including means, standard deviations, and medians for continuous variables and proportions for discrete variables) will be used to summarize data as appropriate.

The trial design is specified because of its practical simplicity, use of a biomarker, and not because of power considerations. The sample size of 20 subjects in a Phase 1b study is considered adequate to evaluate the initial safety, PK/PD, and activity of *acalabrutinib* in this patient population.

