- i. Cycle 1 Day 1 testing does not need to be repeated if screening serum chemistry was done within 7 days of first dose of study drug. Serum chemistry: albumin, alkaline phosphatase, alanine transaminase (ALT), aspartate aminotransferase (AST), bicarbonate, blood urea nitrogen (BUN), calcium, chloride, creatinine, glucose, lactate dehydrogenase (LDH), magnesium, phosphate, potassium, sodium, total bilirubin, total protein, and uric acid.
- j. Urinalysis: pH, ketones, specific gravity, bilirubin, protein, blood, and glucose.
- k. T/B/NK cell count (ie, CD3, CD4, CD8, CD19, CD16/56). During Cycle 5-12, only done end of Cycle 6 and 12.
- l. Serum immunoglobulin: IgG, IgM, IgA. During Cycle 5-12, only done end of Cycle 6 and 12.
- m. A bone marrow aspirate and biopsy will be done at screening. Subjects who have a bone marrow aspirate and biopsy result since completion of their last therapy for DLBCL may use those bone marrow results in lieu of the baseline bone marrow aspirate/biopsy required for this study provided the biopsy/aspirate was done within 60 days before the first dose of study drug. Thereafter, bone marrow aspirate and biopsy will only be required to confirm any complete remission.
- n. Pharmacodynamic (PD) assessments will be done on subjects at sites in the United States. On Cycle 1 Day 1 AND Day 8 the PD samples are drawn predose and 4 hours (\pm 10 minutes) postdose. On Cycle 1 Day 2, Cycle 1 Day 28, and Cycle 2 Day 28, the PD samples are drawn up to 10 minutes predose (ie, the first dose of that day). At the Safety follow-up visit, a PD sample will be collected. Note: Timepoints are relative to the morning dose.
- o. Pharmacokinetic (PK) assessments will be done on subjects at sites in the United States. PK samples for Cycle 1 Day 1 are drawn predose and at 0.5, 1, 2, 4, 6 and 24 h (before first dose on Day 2) postdose. Samples for Cycle 1 Day 8 are drawn predose and at 0.5, 1, 2, 4, and 6 h postdose. On Cycle 1 Day 15, 22, and 28, a PK sample is drawn predose and the second PK sample must be drawn 1 hour postdose. Note: Timepoints are relative to the morning dose.
- p. Available archival tumor tissue is required to be eligible for this study. Either unstained slides (a minimum of 10 slides) or a paraffin block will be acceptable for central pathology review.
- q. ***Acalabrutinib*: For Cycle 1 Day 1, 2, 8, 15, 22, and 28 study drug (first dose of the day) is administered at the site.**

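### Central pathology review of ABC subtype affects none of the analysis sets in Section 5.2, so the reported ORR can include subjects who are not ABC on central review and may understate activity in ABC DLBCL

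*Protocol*

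**What the plan says.** **Entry.** The inclusion criterion in the Synopsis, repeated as criterion 3 in Section 3.4.1, reads "Pathologically confirmed de novo ABC DLBCL, and subjects must have available archival tissue for central pathology review to be eligible". It does not say who confirms the subtype. Section 4.1.5 has the site send the sponsor the "site pathology report for confirming diagnosis of ABC DLBCL" as part of enrollment.

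**Central review.** Section 4.1.6 states "All subjects must have available archival tissue for central pathology review", and footnote p of Appendix 4 states "Available archival tumor tissue is required to be eligible for this study". Both set a condition on tissue, not on a result. The steps in Section 3.4.4 contain no central pathology step, and the turnaround is short: "An Enrollment Confirmation Form will be completed and faxed/emailed to the study center by the sponsor within 24 hours". Section 3.4.3 allows replacement only for not completing Cycle 2.

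**Analysis.** Section 5.2 defines the Safety set as all treated subjects and the ITT population as all enrolled subjects. The PP set is treated subjects who "have sufficient baseline measurements, and undergo ≥ 1 assessment for the endpoint of interest". All three are used for efficacy, except that the Safety set is not used for duration of response (DOR). None depends on subtype.

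**Role of subtype.** The title, the primary objective and Section 5.1 all concern ABC DLBCL. Section 5.4 says "The trial design is specified because of its practical simplicity, use of a biomarker, and not because of power considerations". Section 1.2 cites a phase 2 study of another Btk inhibitor with 41% response in 29 ABC subjects and 5% in 20 GCB subjects.

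**The concern.** The protocol selects on a subtype that, by its own background, goes with a large difference in response to this drug class. It requires the tissue for a second reading of that subtype and then gives the reading no role in the analysis. Followed exactly, Section 5.2 yields an ORR for disease called ABC at the site. That differs from an ORR in ABC DLBCL if the site and central readings disagree. Even the set named per-protocol would keep a subject who, on central review, fails the main histology criterion or meets exclusion 1 or 2 (transformed disease, PMBL).

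What is at stake is the reading of a secondary endpoint in a single-arm trial of 20. If the ORR came out low, the analyses as defined would not show how far this reflects low activity in ABC disease and how far it reflects subjects without ABC disease.

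**Working it through.** **The plan's own figures.** N = 20 comes from no formula, so there is nothing to reproduce. The cited response rates agree with whole counts: 12/29 = 41.4% in ABC (CR 5/29 = 17.2%, PR 7/29 = 24.1%) and 1/20 = 5.0% in GCB.

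**Inputs.** ABC response 0.41 and GCB response 0.05 (Section 1.2); N = 20 (Section 5.4); one-sided 97.5% interval for ORR (Section 5.5.4). The share m of subjects who are GCB-like on central review is not in the protocol. The values below are assumptions.

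**Effect on ORR.** Expected ORR = 0.41(1 − m) + 0.05m. Each such subject lowers it by (0.41 − 0.05)/20 = 1.8 percentage points. The last column is 1 − (1 − m)^20 and treats subjects as independent.

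| Assumed m | Subjects of 20 | Expected ORR | Loss (points) | Expected responders | Chance of at least one |
|---|---|---|---|---|---|
| 0 | 0 | 41.0% | 0 | 8.20 | 0 |
| 5% | 1 | 39.2% | 1.8 | 7.84 | 64% |
| 10% | 2 | 37.4% | 3.6 | 7.48 | 88% |
| 20% | 4 | 33.8% | 7.2 | 6.76 | 99% |
| 30% | 6 | 30.2% | 10.8 | 6.04 | >99% |

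**Against sampling error.** With 8 responders of 20 (40%), the exact one-sided 97.5% lower limit is 19.1%, which is 20.9 points below the estimate. A loss of 3.6 points (m = 10%) is about a sixth of that distance, 7.2 points about a third, and 10.8 points about half.

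**Effect on DOR.** DOR counts responders only. At m = 20%, the 4 GCB-like subjects are expected to supply 4 × 0.05 = 0.2 of 6.76 responders (3.0%). At m = 30%, 6 × 0.05 = 0.3 of 6.04 (5.0%).

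**Effect on PFS.** The protocol gives no PFS by subtype under a Btk inhibitor, so no figure can be derived.

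**What a confirmed subset would show.** Suppose 4 of 20 are not ABC and all 7 responders are ABC. The all-treated ORR is 7/20 = 35.0% (lower limit 15.4%). The confirmed-ABC ORR is 7/16 = 43.8% (lower limit 19.8%). The distance from estimate to limit grows from 19.6 to 24.0 points.

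**The case against.** **Nothing in the text is contradictory.** Local entry with later central review is a legitimate design, and a confirmed-subtype table could sit in a statistical analysis plan that is not shown. The first part stands, and no change to entry is proposed. The second carries less weight, because the protocol itself defines the three sets and assigns them to efficacy. A PP set that ignores the central result is a stated rule, not an omitted detail.

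**The data could be separated anyway.** Tissue is required of every subject, and Section 5.5.6 plans exploratory correlations of subject characteristics with outcome. A reader might infer that a low ORR could never be explained. The documents do not support that: the limit lies in the analyses as defined, not in the data. But Section 5.5.6 is generic and does not mention central subtype.

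**The size is fragile.** This stands. The 41% and 5% are interim results for a different drug. Exact 95% intervals on the implied counts are 23.5% to 61.1% and 0.1% to 24.9%. The protocol does not say how subtype was assigned in that study, so its 41% may already contain some misclassification. The 5% applies to GCB, and no rate is given for transformed disease or PMBL.

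**Activity is secondary.** This also stands. The primary objective is safety, no hypothesis is tested, and the sample size is not based on power. Type I error and power are not in question.

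**Conclusion.** The point holds in a limited form. The central result changes no analysis set, so the efficacy sets can include subjects who are not de novo ABC on central review, and the ORR may then understate activity in ABC DLBCL. Under the assumed shares the loss runs from 1.8 points (5%) to 10.8 points (30%). At 10% or less it is small beside sampling error with 20 subjects. These figures assume that every discordant subject responds at the cited GCB rate and that the cited rates carry over to this drug.

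Two stronger readings are not supported. A reader might infer that misclassified subjects are present; the protocol gives no discordance rate, so this is a possibility only. A reader might also infer that DOR and PFS are diluted along with ORR. The effect on DOR is minor, and that on PFS is unknown in size and direction: the only subtype prognosis in the protocol (Section 1.1, after standard chemotherapy) favors GCB.

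The change is still worth making, because it uses tissue already required and makes the activity estimate match the stated population.

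**What to change.** - In Section 5.2, add central confirmation of de novo ABC DLBCL to the PP definition when that set is used for response. Alternatively, define a separate centrally confirmed ABC efficacy subset.
- Report the ORR in that set, with its interval, beside the all-treated ORR.
- List separately the subjects whose central result is discordant and those whose tissue is inadequate for a result.
- Leave the Safety and ITT sets, and the PP set as used for PK/PD, unchanged.

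The cost is a clause in Section 5.2, one more table column and a short listing. No new sample or procedure is needed. The downside is a smaller confirmed subset with a wider interval, which also loses subjects whose tissue cannot be read; the all-treated result remains on view.

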4.1.6 Archival Tumor Sample

All subjects must have available archival tissue for central pathology review. Either unstained slides (minimum of 10 slides) or a paraffin block will be acceptable for central pathology review. Please refer the study manual for a more detailed description of the procedures and for information on where to send the archival tissue samples.

4.1.7 ECOG Performance Status

The ECOG performance index is provided in [Appendix 1](#).

4.1.8 Physical Examination, Vital Signs, Height & Weight

The screening physical examination will include, at a minimum, the general appearance of the subject, height (screening only) and weight, and examination of the skin, eyes, ears, nose, throat, lungs, heart, abdomen, extremities, musculoskeletal system, nervous system, and lymphatic system.

Symptom-directed physical exams, including tumor assessments by palpation, will be done during the treatment period and at the safety follow-up visits.

Vital signs (blood pressure, heart rate, respiratory rate, and body temperature) will be assessed after the subject has rested in the sitting position.

4.1.9 Bone Marrow Aspirate and Biopsy

A bone marrow aspirate and biopsy will be done at screening. Subjects who have a bone marrow aspirate and biopsy result since completion of their last therapy for DLBCL may use those bone marrow results in lieu of the baseline bone marrow aspirate/biopsy required for this study provided the biopsy/aspirate was done within 60 days of the first dose of study drug. Per the current response criteria ([Cheson 2014](#)), a bone marrow aspirate/biopsy will also be required at any time on study to confirm complete remission (CR). A bone marrow aspirate and biopsy will also be done at end of Cycle 12. Testing will be performed at the study center's local laboratory or other clinical laboratory listed on the investigator's form FDA 1572. De-identified copies of all bone marrow biopsy/aspirate results may be requested by the sponsor.

4.1.10 Electrocardiogram

Subjects should be in supine position and resting for ≥ 10 minutes before study-related ECGs.

4.1.11 Urine Pregnancy Test

Pregnancy tests will be required only for women with childbearing potential. If positive, pregnancy must be ruled out by ultrasound. Testing will be done by the central laboratory.

4.1.12 Hematology

Hematology studies must include complete blood count (CBC) with differential and platelet and reticulocyte counts. Testing will be done by the central laboratory.

4.1.13 Serum Chemistry

Chemistry must include albumin, alkaline phosphatase, ALT, AST, bicarbonate, blood urea nitrogen (BUN), calcium, chloride, creatinine, glucose, lactate dehydrogenase (LDH), magnesium, phosphate, potassium, sodium, total bilirubin, total protein, and uric acid. If an unscheduled ECG is done at any time, then an electrolyte panel (ie, calcium, magnesium, and potassium) must be done to coincide with the ECG testing. Testing will be done by the central laboratory.

4.1.14 Urinalysis

Urinalysis includes pH, ketones, specific gravity, bilirubin, protein, blood, and glucose. Testing will be done by the central laboratory.

4.1.15 T/B/NK Cell Count

Flow cytometry testing will include CD3⁺, CD4⁺, CD8⁺, CD19⁺, and CD16/56⁺ cells. Testing will be done by the central laboratory.

4.1.16 Serum Immunoglobulin

Testing for IgG, IgM, and IgA will be done by the central laboratory.

4.1.17 Hepatitis B and C Testing

Hepatitis serology testing must include hepatitis B surface antigen (HBsAg), hepatitis B surface antibody (HBsAb), anti-HBc, and hepatitis C (HCV) antibody. Since intravenous immunoglobulins (IVIG) may cause false positive hepatitis serology, subjects who are receiving prophylactic IVIG and have positive HBsAg or anti-HBc must have negative hepatitis B DNA to be eligible. In addition, any subjects testing positive for any hepatitis serology, must have PCR testing (see [Appendix 4](#) and exclusion criterion #13). Testing will be done by local or central laboratory.

Refer to [Section 3.7.4.1](#) and [Appendix 4](#) regarding monitoring of subjects who are anti-HBc positive or have a known history of HBV.

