3.4.2 Exclusion Criteria

Subjects will be ineligible for this study if they meet **any** of the following criteria:

1. Transformed DLBCL or DLBCL with coexistent histologies (eg, FL or MALT)
2. Primary mediastinal (thymic) large B-cell lymphoma (PMBL)
3. Known central nervous system (CNS) lymphoma
4. Prior malignancy, except for adequately treated basal cell or squamous cell skin cancer, in situ cervical cancer, or other cancer from which the subject has been disease free for ≥ 2 years or which will not limit survival to < 2 years. Note: these cases must be discussed with the medical monitor.
5. A life-threatening illness, medical condition, or organ system dysfunction which, in the investigator's opinion, could compromise the subject's safety, interfere with the absorption or metabolism of *acalabrutinib*, or put the study outcomes at undue risk.
6. Significant cardiovascular disease such as uncontrolled or symptomatic arrhythmias, congestive heart failure, or myocardial infarction within 6 months of screening, or any Class 3 or 4 cardiac disease as defined by the New York Heart Association Functional Classification, or QTc > 480 msec.
7. Malabsorption syndrome, disease significantly affecting gastrointestinal function, or resection of the stomach or small bowel, gastric bypass, symptomatic inflammatory bowel disease, or partial or complete bowel obstruction.
8. Any immunotherapy within 4 weeks of first dose of study drug.
9. The time from the last dose of the most recent chemotherapy or experimental therapy to the first dose of study drug is < 5 times the half-life of the previously administered agent(s).
10. Radio- or toxin-immunoconjugates within 10 weeks of the first dose of study drug
11. Prior exposure to a B-cell receptor (BCR) inhibitor (eg, Btk phosphoinositide-3 kinase [PI3K], or Syk inhibitors) or BCL-2 inhibitors (eg, ABT-199).
12. Grade ≥ 2 toxicity (other than alopecia) continuing from prior anticancer therapy including radiation.
13. Known history of human immunodeficiency virus (HIV), serologic status reflecting active hepatitis B or C infection, or any uncontrolled active systemic infection. Subjects with hepatitis B core antibody positive who are surface antigen negative or who are hepatitis C antibody positive will need to have a negative PCR result before enrollment. Those who are hepatitis B surface antigen positive or hepatitis B PCR positive and those who are hepatitis C PCR positive will be excluded.

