- r. A pretreatment CT scan with contrast (unless contraindicated) is required of the chest, abdomen, and pelvis and any other disease sites (eg, neck) within 30 days before the first dose of study drug. A pretreatment positron-emission tomography (PET)/CT scan within 90 days before the first dose is also required. Information on extranodal involvement will also be recorded. During treatment, CT scans with contrast (unless contraindicated) of the chest, abdomen, and pelvis and any other disease sites (eg, neck) will be done for tumor assessments at the end of Cycle 2 (\pm 7 days), Cycle 4 (\pm 7 days), and Cycle 6 (\pm 7 days); and then every 3 cycles (12 weeks, \pm 7 days) thereafter or more frequently at investigator discretion. At all other visits, tumor assessments will be done by physical exam and laboratory results. Bone marrow and PET/CT are only required for confirmation of CR per clinical guidelines (see [Section 4.2](#)). At all other visits tumor assessments will be done by physical exam and laboratory results.
- s. Subjects who discontinue study therapy will continue on study for follow-up of safety and time-to-next therapy for DLBCL unless they withdraw consent for further follow-up.
- t. The indicated samples at this timepoint (Cycle 1 Day 1) must be drawn predose.
- u. Hepatitis serology must include hepatitis B surface antigen (HBsAg), hepatitis B core antibody (anti-HBc), and hepatitis C (HCV) antibody. Subjects who are receiving prophylactic intravenous immunoglobulins (IVIG) and have positive HBsAg or anti-HBc must have negative hepatitis B DNA to be eligible. In addition, any subjects testing positive for any hepatitis serology, must have polymerase chain reaction (PCR) testing (see exclusion criterion #13).
- v. Subjects who are anti-HBc positive (or have a known history of HBV infection) should be monitored monthly with a quantitative PCR test for HBV DNA. Monthly monitoring should continue until 12 months after last dose of *acalabrutinib*. Any subject with a rising viral load (above lower limit of detection) should discontinue *acalabrutinib* and have antiviral therapy instituted and a consultation with a physician with expertise in managing hepatitis B.

Appendix 5. Actions Required in Cases of Increases in Liver Biochemistry and Evaluation of Hy's Law

INTRODUCTION

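### For subjects on prophylactic IVIG, Section 4.1.17 and Appendix 4 footnote u make HBsAg positivity conditional on negative HBV DNA, while exclusion criterion 13 and the synopsis bar it outright

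*Protocol*

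**What the plan says.** Four places in the protocol state an eligibility rule that involves HBsAg.

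- **Section 3.4.2, criterion 13.** The closing sentence reads "Those who are hepatitis B surface antigen positive or hepatitis B PCR positive and those who are hepatitis C PCR positive will be excluded". For hepatitis B, the route through a negative PCR is limited to "Subjects with hepatitis B core antibody positive who are surface antigen negative". The lead-in to the list, "Subjects will be ineligible for this study if they meet" any of the criteria, makes each one sufficient to exclude.
- **Study Synopsis, Exclusion Criteria.** The same rule in the same words. Neither this nor criterion 13 mentions IVIG or any exception.
- **Section 4.1.17.** "subjects who are receiving prophylactic IVIG and have positive HBsAg or anti-HBc must have negative hepatitis B DNA to be eligible". The reason is given in the same sentence: "Since intravenous immunoglobulins (IVIG) may cause false positive hepatitis serology".
- **Appendix 4, footnote u.** "Subjects who are receiving prophylactic intravenous immunoglobulins (IVIG) and have positive HBsAg or anti-HBc must have negative hepatitis B DNA to be eligible".

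In both Section 4.1.17 and footnote u, the next sentence requires PCR testing after any positive hepatitis serology and points the reader to criterion 13. Section 4.1.5 says that eligibility is assessed under Section 3.4.

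**The concern.** Section 4.1.17 and footnote u treat positive HBsAg in an IVIG recipient as a result that the HBV DNA test settles. Criterion 13 and the synopsis treat it as an exclusion that no DNA result can lift. A site working from the schedule footnote or the testing section could reasonably conclude that an HBsAg-positive, DNA-negative subject on IVIG may be enrolled.

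What is at stake is safety. Section 3.7.4.1 describes reactivation of viral hepatitis on acalabrutinib as potentially serious or life-threatening, and the HBsAg bar is there to guard against it. The site's own reading carries weight for two reasons. Hepatitis testing need not be central: "Testing will be done by local or central laboratory". And hepatitis results are not among the items that Section 4.1.5 lists for submission to the sponsor at enrolment.

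**Working it through.** No figure in the protocol is in question, so the check is a comparison of text.

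**Step 1: count the places.** Criterion 13, synopsis, Section 4.1.17 and footnote u make 4. Two of the 4 (criterion 13, synopsis) bar HBsAg positivity outright. The other two (Section 4.1.17, footnote u) word it as conditional on negative HBV DNA, for IVIG recipients only.

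**Step 2: apply both rules to a subject on prophylactic IVIG.**

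| Serology | HBV DNA | Criterion 13 and synopsis | Section 4.1.17 and footnote u | Agree? |
|---|---|---|---|---|
| HBsAg negative, anti-HBc positive | negative | not excluded on this ground | condition met | yes |
| HBsAg negative, anti-HBc positive | positive | excluded | condition not met | yes |
| HBsAg positive | positive | excluded | condition not met | yes |
| HBsAg positive | negative | excluded | condition met | **no** |

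The conflict is confined to the last row. For anti-HBc-positive, HBsAg-negative subjects all four places agree.

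**Step 3: ask which rule prevails.** Three things favour criterion 13: any single criterion excludes (Section 3.4.2), eligibility is assessed under Section 3.4 (Section 4.1.5), and the sentence after the IVIG sentence refers back to criterion 13. That cross-reference belongs to the PCR-testing requirement, however (in footnote u: "must have polymerase chain reaction (PCR) testing (see exclusion criterion #13"). No sentence says expressly which rule wins for an HBsAg-positive IVIG recipient.

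**Step 4: test whether the texts can be reconciled.** Suppose negative DNA is necessary but not sufficient, and criterion 13 still excludes. Then naming HBsAg in the IVIG sentence does nothing, because the subject is out whatever the DNA result. The stated reason also fails for HBsAg: a DNA test to sort out a false positive serves no eligibility purpose if its result cannot change the outcome.

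**Step 5: look at the safeguards.** Section 4.1.5 lists 3 items for the sponsor at enrolment: screening radiology results, the site pathology report, and prior therapies with best responses. None of the 3 is a hepatitis result. The protocol does not describe the content of the Enrollment Confirmation Form. Monthly HBV DNA monitoring under Section 3.7.4.1 and footnote v is triggered by anti-HBc positivity or a known history of HBV infection. It would therefore not reach an HBsAg-positive, anti-HBc-negative subject with no known history, but such a subject is on study only if criterion 13 has already been misapplied.

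**The case against.** The best reply is that there is no strict contradiction. The IVIG sentence states a requirement, not an entitlement: it says what such a subject must show and waives nothing in criterion 13. A site can obey all four places by running the DNA test and then applying criterion 13. To enrol wrongly, it would have to overlook a numbered exclusion criterion cited in the very next sentence. Section 3.4.4 also puts the sponsor in the path: contact before screening, a completed form at enrolment, and sponsor notification before treatment. That hepatitis results are not reviewed is an inference from silence.

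Much of this stands. Criterion 13 does govern on a strict reading, a sponsor check cannot be ruled out, and the harm requires a prior error by the site. What it does not do is give the words *HBsAg or* any function, or square them with the false-positive rationale printed beside them. Text that serves a purpose only if an exception exists will be read as granting one.

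Two objections concern the remedy. After the deletion, an HBsAg-positive subject would still be sent for PCR under the next sentence. That is true, but that sentence only orders a test and offers no route to eligibility. The shortened IVIG sentence would also largely repeat criterion 13, which already requires a negative PCR from anti-HBc-positive, HBsAg-negative subjects with or without IVIG. That is also true, and harmless.

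**Conclusion.** The inconsistency is real, and its weight is low. Two of the four places bar HBsAg positivity and two make it conditional. They give different answers for one type of subject: on prophylactic IVIG, HBsAg positive, HBV DNA negative. The protocol does not say how many subjects will be on IVIG, so the number affected among the 20 planned is unknown and may be 0. No endpoint, analysis or sample-size figure depends on it.

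The conclusion assumes that criterion 13 and the synopsis express the sponsor's intention. The hepatitis B monitoring rules are adequate if criterion 13 is applied as written. The point is worth correcting because the ambiguity sits on a safety exclusion and is cheap to remove.

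**What to change.** Delete the words *HBsAg or* from the IVIG sentence in Section 4.1.17 and in Appendix 4 footnote u. The sentence then names only anti-HBc, for which criterion 13 and the synopsis already require a negative PCR, and all 4 places agree with the governing criterion.

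The cost is 2 words × 2 places = 4 words at the next amendment. No testing is added, and no one's eligibility under criterion 13 changes.

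If the sponsor does want an exception for IVIG recipients with a suspected false-positive HBsAg, the change belongs in criterion 13 and the synopsis, as an explicit exception. The deletion is the conservative choice because it leaves the stated exclusion intact.
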